### 8.3. Exclusion Criteria

Patients who meet any of the following criteria will be excluded from study entry:

1. Patients with any other prior malignancy are not allowed except for the following:
  - a. Adequately treated basal cell or squamous cell skin cancer
  - b. In situ cervical cancer
  - c. Adequately treated Stage I or II cancer from which the patient is currently in complete remission or other cancer from which the patient has been disease-free for 2 years.
2. Uncontrolled CNS metastases or treatment by neurosurgical resection, radiation or brain biopsy within 4 weeks prior to Day 1.
3. Prior treatment with an anti-PD-1, anti-PD-L1, anti-PD-L2, anti-CTLA-4 antibody, or any other antibody or drug specifically targeting T-cell co-stimulation or immune checkpoint pathways.
4. Any of the following prior therapies:
  - a. Chemotherapy  $\leq$  3 weeks prior to registration;
  - b. Biologic therapy  $\leq$  4 weeks prior to registration;
  - c. Radiation therapy  $\leq$  3 weeks prior to registration;
  - d. Investigational therapy  $\leq$  4 weeks prior to registration.
5. Failure to fully recover from acute, reversible effects defined as  $\leq$  grade 1 CTCAE v.4.03 of prior systemic therapy regardless of interval since last treatment.
6. Other concurrent investigational therapy (utilized for a non-FDA-approved indication and in the context of a research investigation).
7. Any of the following because this study involves an agent that has known genotoxic, mutagenic and teratogenic effects:
  - a. Pregnant women
  - b. Nursing women
  - c. Men or women of childbearing potential who are unwilling to employ adequate contraception during treatment and 8 weeks following the completion of study drug treatment.
8. Patients with active, known or suspected autoimmune disease. Exceptions are vitiligo, type I diabetes mellitus, residual hypothyroidism due to autoimmune condition only requiring hormone replacement, psoriasis not requiring systemic treatment, or conditions not expected to recur in the absence of an external trigger.
9. Patients with a condition requiring systemic treatment with either corticosteroids ( $> 10$  mg daily prednisone equivalent) or other immuno-suppressive medications within 14 days of study drug administration. Inhaled or topical steroids, and adrenal replacement doses  $> 10$  mg daily prednisone equivalents are permitted in the absence of active autoimmune disease.
10. History of organ transplantation.

11. Receiving therapeutic anticoagulation (warfarin, low molecular weight heparin, or other novel oral anticoagulants).
12. Requiring blood product support.
13. Positive test for hepatitis B virus surface antigen (HBV sAg) or hepatitis C virus ribonucleic acid (HCV RNA), or human immunodeficiency virus (HIV1 or 2) indicating acute or chronic infection.
14. Active infection (any grade)  $\leq$  5 days prior to registration.
15. History of tuberculosis or history of Mantoux PPD positivity.
16. Co-morbid systemic illnesses or other severe concurrent disease which, in the judgment of the investigator, would make the patient inappropriate for entry into this study or interfere significantly with the proper assessment of safety and toxicity of the prescribed regimens.
17. Current exposure to household contacts  $\leq$  15 months old or household contact with known immunodeficiency.
18. Unwillingness to avoid household contacts  $\leq$  15 months old or household contact with known immunodeficiency 1 week after treatment.
19. Allergy to measles vaccine or history of severe reaction to prior measles vaccination.
20. Allergy to iodine. **Note:** This does not include reactions to intravenous contrast materials

#### **8.4. Removal of Patients from Study**

Withdrawal of a patient from the study means that no further study visits or procedures are performed and no further data are collected. Every reasonable effort will be made to keep the patient in the study; however, in the event that a patient is withdrawn from the study, every effort will be made by the investigator to complete and report the reasons for withdrawal as thoroughly as possible. The reason for termination must be clearly documented on the appropriate page of the CRF. Study withdrawal should include the final assessments, as required by the protocol and every effort should be made to perform the study follow-up procedures (e.g., laboratory tests, physical examination including an evaluation of toxicity/adverse events).

A termination CRF must be completed for all enrolled patients.

The patient may be withdrawn from the study for any of the following reasons.

- Voluntary withdrawal by patient
- Patient lost to follow-up
- Termination of the study by sponsor
- Patient death

If a patient dies, Vyriad will actively seek to determine the date and cause of death.

If there is an ongoing toxicity associated with MV-NIS, patients must be followed with appropriate medical management until resolution or stabilization.

A reasonable effort should be made to contact any patient who is lost to follow-up during the course of the study in order to complete assessments and retrieve any outstanding data. If a patient is unreachable by telephone after three (3) attempts, the minimum of a registered letter should be sent requesting that the patient make contact with the investigator.

### **8.5. Replacement of Patients in Study**

A patient who discontinues from the trial during the active treatment for reasons other than AE/SAE, or disease progression can be replaced.

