### **7.1.2. Conduct of escalation cohorts**

A standard 3+3 design will be used for the dose escalation part of the study. Starting at dose level 1 (refer to [Table 3](#)), three patients will be treated per dose level. The first three patients treated at dose level 1 will be enrolled at least 24 hours apart. All patients will be observed for a DLT period of 36 days after MV-NIS administration (which is 3 weeks after atezolizumab) and the last patient in each cohort must have completed the DLT period prior to each dose escalation decision. Resolution of viremia in all patients at a dose level is required prior to dose escalation being allowed.

If a DLT is observed, 3 additional patients will be enrolled at that dose level. If 1/6 patients experiences DLT, escalation may proceed; if  $\geq 2/6$  patients experience DLT, the MV-NIS dose will be de-escalated and 3 further patients added at the previous dose level. Dose level -1 will only be explored if dose level 1 is not tolerated. Doses will not be escalated in any individual patient. Any patient who experiences a DLT will be taken off study drugs, but will be followed up for response and PFS.

If no DLTs are seen at any of the dose levels, then the MTD will be the maximum delivered dose ( $1 \times 10^9$ ). MTD will be defined as the highest safely administered dose at which no more than one out of six or 0/3 patients experience DLT.

The first 6 patients of the expansion cohort will be enrolled and observed for 36 days after the 6th patient has received treatment prior to any additional patients being treated. If  $\leq 1/6$  DLT is observed then the remaining patients will be enrolled and treated sequentially, with no waiting period or limitation on simultaneous enrolment. If  $\geq 2/6$  patients in the expanded cohort experience a DLT, then the entire expansion cohort will be re-enrolled at the next lower dose level.

If a patient fails to complete the initial course of therapy (defined as study drug administration and four weeks of observation) for reasons other than adverse events or disease progression based on the day 36 CT-scan, then the patient will be regarded as non-evaluable for DLT and an additional patient will be treated at the current dose level. However, all AE information from patients who received any study treatment will be utilized in the analysis.

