#### **9.1.7.1. Study Drug Discontinuation**

Discontinuation of a patient from study means that no further MV-NIS or atezolizumab will be administered but the remaining study visits or procedures are performed and follow-up data are collected.

A patient may be discontinued for any of the following reasons:

- Progression of disease (see [Section 10](#))
- An AE requires permanent discontinuation of study drug
- Voluntary withdrawal by patient
- Protocol deviation
- Patient lost to follow-up
- Patient death
- Termination of study by sponsor.

Patients whose study drug is discontinued due to toxicity are to be followed until there is either:

- Resolution or stabilization to baseline or Grade 1
- The patient is lost to follow-up
- The event is otherwise explained.

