## 10. EFFICACY ASSESSMENTS

RECIST version 1.1 will be used in this study for assessment of tumor response. While either CT or MRI may be utilized as per RECIST 1.1, CT is the preferred imaging technique in this study.

Tumor measurements for efficacy evaluation will be done 5 weeks (36 day visit) after IT injection of the study drug and then every 3 cycles (i.e. cycles 4, 7, 10 etc.) until PD thereafter. A radiological assessment of CR or PR requires confirmatory imaging at least 4 weeks after the initial assessment of response was observed.

If there is suspicion of disease progression based on clinical or laboratory findings before the next scheduled assessment, an unscheduled assessment should be performed. Patients with a global deterioration of health status requiring discontinuation of treatment without objective evidence of disease progression at that time should be reported as “symptomatic deterioration”. Every effort should be made to document objective progression even after discontinuation of treatment.

For patients whose disease progresses, immune-related response criteria per irRECIST may be used by the investigator to continue therapy in the presence of potential pseudoprogression or tumor flare with clinical stability as appropriate until PD is confirmed.

For clinically stable patients, if imaging shows PD, treatment may be continued at the discretion of the investigator and tumor assessment should be repeated  $\geq$  9 weeks later to confirm or refute PD.

Clinically stable is defined by the following criteria:

- Absence of signs and symptoms indicating disease progression
- No decline in ECOG performance status
- Absence of rapid progression of disease
- Absence of progressive tumor at critical anatomical sites (e.g., cord compression) requiring urgent alternative medical intervention.

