## 13. STATISTICAL CONSIDERATIONS

### 13.1. General Design

This study will employ the standard “3+3” design for phase 1 clinical trials ([Storer 1989](#); [Simon 1997](#)) and as such no formal statistical analysis is planned for the escalation part of the study.

For the expansion cohort, the sample size calculation is based on a method proposed by Cancer Research UK for small oncology studies ([Khan 2012](#)). Based on data with atezolizumab in the unselected metastatic NSCLC population, the null hypothesis is set at an ORR of 20%, with the target ORR for the combination of 45%. With an  $\alpha=0.043$  and 80.29% power, at least 8 responses in 21 patients are needed to show success.

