#### 13.1.1. Analysis populations

Safety Population: The safety population consists of all patients who receive at least one dose of the study medication. All safety and tolerability evaluations will be based on this analysis set.

PK/PD Population: The PK/PD population includes all patients without protocol deviations affecting interpretability of PK and/or PD.

Efficacy Population: primary efficacy analyses will utilize the treated population at the MTD, meaning all patients who receive at least 1 dose of study drug at the MTD; an additional analysis will include all treated patients, which is identical to the Safety Population.

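### Section 8.5 sets no time limit on replacing patients, and a replacement on top of the planned 21 at the MTD leaves the 8-response success rule without a valid cut-off

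*Combined protocol and SAP*

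**What the plan says.** **Replacement.** Section 8.5 is one sentence: "A patient who discontinues from the trial during the active treatment for reasons other than AE/SAE, or disease progression can be replaced". It gives no purpose, time limit, decision-maker or analysis rule, and the protocol does not define active treatment. Section 7.1.2, repeated in the synopsis, has a narrower rule. It covers a patient who does not complete dosing plus four weeks of follow-up, for reasons other than adverse events or progression: "then the patient will be regarded as non-evaluable for DLT and an additional patient will be treated at the current dose level".

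**Reasons for stopping.** Section 9.1.7.1 lists, among others, voluntary withdrawal, loss to follow-up and "Protocol deviation". Section 8.5 excludes none of these three.

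**Timing and knowledge.** Section 7.1.1 continues atezolizumab until progression, toxicity or withdrawal of consent. Section 9.1.4 says the study is open label. Section 10 places the first efficacy scan at day 36 and later ones every three cycles.

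**Analysis.** Section 13.1.1 defines the primary efficacy population as those treated at the MTD, "meaning all patients who receive at least 1 dose of study drug at the MTD". Section 13.1 sets a null ORR of 20%, a target of 45%, alpha 0.043 and power 80.29%, and states that "at least 8 responses in 21 patients are needed to show success". It gives no cut-off for any other number of patients. Sections 7.1 and 7.1.3 size the expansion (15 to 18 patients) so that the MTD total is 21.

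**The concern.** The success rule is a fixed count tied to a fixed number of patients. Each further patient dosed at the MTD is a new chance to reach 8 responses, while a non-responder who is replaced takes none away.

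Replacement within the first four weeks does little harm, because it is decided before the day 36 scan. The wider reach of Section 8.5 is the difficulty. Treatment is open-ended, so a patient who withdraws, is lost or is taken off for a deviation at a later cycle may still count as being on active treatment. By then the investigator and sponsor know whether that patient has responded, and replacement is optional. The decision can therefore depend on the outcome that the rule tests.

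At stake is the stated error rate of the protocol's only formal success rule, which is also the basis of its sample size.

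**Working it through.** **Inputs.** From Section 13.1: N = 21, cut-off r = 8, null ORR p0 = 0.20, target ORR p1 = 0.45. Sidedness is not stated; the exact one-sided upper tail reproduces the figures. The documents give no dropout rate, so the number of replacements and the probability d below are assumptions.

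**1. The plan's own figures.** With X binomial(N, p):
- alpha = P(X ≥ 8 | 21, 0.20) = 0.0431 (stated 0.043)
- power = P(X ≥ 8 | 21, 0.45) = 0.8029 (stated 80.29%)

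Both reproduce.

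**2. Replacements absorbed within 21.** If everyone dosed at the MTD counts towards 21 and the expansion enrols fewer to compensate, at most 21 patients can respond. Alpha is then at most 0.0431.

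**3. Replacements on top of 21, cut-off left at 8.** One extra patient turns a failure into a success only if the first 21 gave exactly 7 responses and the extra patient responds:
- P(X = 7 | 21, 0.20) = 116,280 × 0.2^7 × 0.8^14 = 0.0655
- added error = 0.0655 × 0.20 = 0.0131
- alpha = 0.0431 + 0.0131 = 0.0561, from unrounded terms

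The same tail for each N:

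| N at MTD | alpha, cut-off 8 | power, cut-off 8 |
|---|---|---|
| 21 | 0.0431 | 0.803 |
| 22 | 0.0561 | 0.848 |
| 23 | 0.0715 | 0.885 |
| 24 | 0.0892 | 0.914 |

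These are upper bounds, because they give every patient, replaced or not, a full chance to respond. If the replaced patients had none, only 21 can respond and alpha stays at 0.0431.

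**4. Replacement that depends on outcome.** Suppose each non-responder leaves for a qualifying reason with probability d, every such patient is replaced, and responders stay. A replaced non-responder contributes no response, so the count comes from 21 patients who did not leave, each a responder with probability

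p* = p0 / [p0 + (1 − p0)(1 − d)].

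| d (assumed) | p* | P(X ≥ 8 \| 21, p*) |
|---|---|---|
| 5% | 0.20/0.96 = 0.2083 | 0.053 |
| 10% | 0.20/0.92 = 0.2174 | 0.066 |
| 15% | 0.20/0.88 = 0.2273 | 0.083 |
| 20% | 0.20/0.84 = 0.2381 | 0.104 |

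These hold with replaced patients kept in the efficacy set, since the criterion is a count and not a percentage.

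**5. A cut-off that fits the actual N.** With 9 responses required:

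| N | alpha | power at 45% |
|---|---|---|
| 22 | 0.020 | 0.72 |
| 23 | 0.027 | 0.78 |
| 24 | 0.036 | 0.83 |
| 25 | 0.047 | 0.87 |

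**The case against.** The case against is substantial, and several parts of it stand.

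- **The total is fixed.** Sections 7.1 and 7.1.3 make the expansion the balancing figure. A reader might infer that every replacement at the MTD takes the set past 21. The text does not say so: a replacement made while the expansion is enrolling can be offset by enrolling one fewer. The problem is confined to replacements on top of 21, which neither section rules out.
- **Nobody may be dropped.** A reader might infer that a replaced patient leaves the denominator. Section 13.1.1 keeps everyone dosed at the MTD, and no section permits removal.
- **No contradiction.** A reader might take Section 7.1.2 as limiting Section 8.5. It is a DLT-evaluability rule and never says that no other replacement is allowed. The two differ in scope and are not reconciled.
- **Some exits are closed.** Symptomatic deterioration might seem to qualify, because Section 10 reports it separately from objective progression. Section 11.4.11 lets it count, in rare cases, as clinical progression and sends doubtful events to adverse event reporting. Sections 9.3.1 and 9.3.2 treat a patient who needs other anti-cancer therapy as progressed. What remains is mainly voluntary withdrawal, loss to follow-up and protocol deviation, at an unknown rate.
- **Early dropouts do no harm to alpha.** A patient who leaves within four weeks and cannot respond leaves it at 0.043.
- **The endpoint is secondary.** ORR is a secondary objective (Section 6.2), and Section 13.1.6 summarises it descriptively.

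These points narrow the concern but do not remove it. An optional, untimed rule, used as written on a patient already scanned, can break the stated alpha.

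**Conclusion.** The point holds in a limited form and merits a wording change. Section 8.5 can be read to allow optional replacement after tumor results are known, and Section 13.1 has no cut-off for an MTD set larger than 21. If replacements come on top of 21 and the cut-off stays at 8, alpha is at most 0.056 with one, 0.072 with two and 0.089 with three, against 0.043. With outcome-dependent replacement it runs from 0.053 to 0.104 for d from 5% to 20%.

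This rests on three assumptions: active treatment includes the whole atezolizumab period (reasonable, but an inference from an undefined term); replacements are added to the 21 and not absorbed; and the replaced patients had some chance to respond. Where either of the last two fails, alpha does not exceed 0.043. The number of replacements and d are not in the documents.

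The effect is on the secondary ORR success rule only. The MTD decision is untouched.

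**What to change.** **Section 8.5.** Limit replacement to DLT evaluability, in the escalation cohorts and the first 6 expansion patients, decided before any post-baseline tumor scan is reviewed. Section 7.1.2 ties its progression exception to the day 36 CT scan, so that clause needs aligning with this timing.

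**Section 13.1.** State that all patients dosed at the MTD, replaced or not, count towards the 21 and stay in the ORR denominator, as non-responders if they have no confirmed response. If the set still exceeds 21, use the cut-off for the actual N: 9 responses for 22 to 25 patients.

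**Cost.** A few lines of text and no extra patients. The observed ORR will be slightly lower, and some power is lost:
- If one of the 21 had no chance to respond, the 8-response rule has power P(X ≥ 8 | 20, 0.45) = 0.75; with two such patients it is 0.68.
- The 9-response rule has power 0.72 at N = 22 and 0.78 at N = 23. If the one replaced patient at N = 22 had no chance to respond, only 21 can: power is P(X ≥ 9 | 21, 0.45) = 0.66 and alpha 0.014.

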## 9. STUDY DRUG

### 9.1. MV-NIS

MV-NIS is a live, tissue culture adapted measles virus engineered to express the human thyroïdal sodium iodide symporter (NIS). The virus was constructed by inserting the NIS gene (cDNA) into a full-length infectious molecular clone of an attenuated Edmonston lineage measles virus (MV-tag). This virus is not a vaccine. MV-NIS propagates on Vero cells with kinetics equivalent to the parental strain of virus. It propagates selectively in human cancer cells that it infects by binding preferentially to CD46, a membrane protein that is overexpressed in tumor cell lines.

The virus is directly cytopathic to tumor cells leading to the formation of multinucleated syncytia that die by apoptosis. MV-NIS infected tumor cells express NIS, a membrane ion channel that actively transports iodide into cells. Radioiodine uptake by cells expressing NIS provides the basis for in vivo radioiodine imaging that can reveal the profile of MV-NIS gene expression and the location of MV-NIS infected cells during virus spread and elimination.

#### 9.1.1. Preparation and Storage

MV-NIS will be prepared at the Viral Vector Production Laboratory of the Department of Molecular Medicine and stored at  $\leq -65^{\circ}\text{C}$ . The virus will be thawed and mixed with NS immediately prior to administration.

MV-NIS will be stored in an alarmed, temperature-monitored, secure freezer with restricted access. It will be required that the freezer be on a circuit equipped with a backup generator. MV-NIS will be stored in clearly-labeled vials within secondary packaging at or below  $-65^{\circ}\text{C}$  with appropriate bio-hazard labeling (indicating the nature of the agent) on the freezer door and the door of the room.

The MV-NIS will be prepared under biosafety level 1 guidelines in pharmacy under the direction of an appropriately trained pharmacist. All surfaces must be cleaned with 70% isopropyl alcohol before and after use. All equipment not dedicated for the study use will be sterilized or cleaned using 10% bleach solution, followed by 70% isopropyl alcohol before subsequent use. Sterile normal saline will be used to dilute the investigational product. See study specific Pharmacy Manual for details.

#### 9.1.2. Handling and Thawing

BSL-1 infection control policies should be utilized for preparation, transport, and disposal of the investigational product. Appropriate gowns, gloves, safety glasses with side shields or face shields should be worn at all times during handling.

Thawing should occur at room temperature with the vial(s) upright. Hot water baths should not be used. Thaw time at room temperature is approximately 10 minutes. After MV-NIS is thawed it must be stored on ice or refrigerated ( $2-8^{\circ}\text{C}$ ) until virus preparation begins. Injection should not occur until the virus is fully thawed. Injection should also not be performed if the virus formulation has been thawed for more than 2.5 hours. The study Pharmacy Manual contains detailed instructions on proper handling, thawing and preparation of MV-NIS for clinical administration.

### 9.1.3. Spills or Environmental Contamination

In the event of a spill, people in the immediate area will be alerted and other institutional personnel will be notified as required by institutional policies. The spill area will be contained by limiting non-essential traffic in the area and using barriers to prevent the flow of material beyond the local area. Personnel that are involved in the cleanup of the spill will wear gloves, gown, surgical/procedure mask and safety glasses with side shields. Aerosols will be allowed to settle before paper towels or lab diapers are placed carefully over the spill. Spills must be absorbed.

For best results, cover the spill area with paper towels and apply a 10% bleach solution (1:10 dilution of commercial chlorine bleach, e.g. Clorox). Start application from the outer perimeter and work inwards. Allow contact with bleach for 20-30 minutes. Fresh paper towels soaked in 10% bleach solution will then be used to wipe the spill area. Area should then be wiped down with paper towels soaked in a 70% ethanol solution to remove bleach that can corrode surfaces if not removed. All waste items will be disposed per institutional policies. Refer to local institutional guidelines for BSL-1 agents.

